6.6 Concomitant Therapy

6.6.1 Prohibited Treatments

- Non study use of adalimumab, or a biosimilar of adalimumab, are prohibited (exclusion criterion 13).
- Any biologic treatment for psoriasis, or any experimental (biological or nonbiological) therapy (within or outside of a clinical study), except for investigational product, for subjects are prohibited (exclusion criteria 13 and 15).
- Treatments (exclusion criterion 16) which include nonbiologic systemic psoriasis therapy (including but not limited to apremilast [within 2 weeks prior to enrollment] oral retinoids, methotrexate, cyclosporine, systemically administered calcineurin inhibitors, azathioprine, thioguanine, hydroxyurea, fumarates, mycophenolate mofetil, Janus kinase inhibitors, or oral or parenteral corticosteroids including intramuscular or intraarticular administration [exception: ophthalmic, otic, nasal, or inhaled corticosteroids within recommended doses is permitted]).
- Any other non study treatment for psoriasis, including UVA or UVB phototherapy and excimer laser (exclusion criterion 17) and topical therapies for psoriasis (except for those specifically allowed exclusion criterion 18) are prohibited.
- Live viral or live bacterial vaccination (exclusion criterion 19).

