A subject may be discontinued from the study at any time at the discretion of the investigator for safety, behavioral, or administrative reasons, including, but not limited to:

Requirement for alternative therapy per the investigator's determination

Clinical Study Protocol: 20200497

Final 1.0 Date: 03 Jun 2021 Page **42** of **87**

 The subject develops a malignancy (exception: subjects may be allowed to continue if they develop no more than 2 non-melanoma skin cancers during the study)

- Adverse events or serious adverse events
- Any laboratory abnormalities that in the judgment of the investigator, taking into consideration the subject's overall status, prevents the subject from continuing participation in the study
- Any other reason relating to the subject's safety or integrity of the study data
- Noncompliance with study procedures
- Withdrawal of consent from the study
- Lost to follow-up
- Decision by sponsor/investigator
- Death

Refer to the Schedule of Assessments (Table 1-1) for data to be collected at the time of study discontinuation and evaluations that need to be completed.

If a subject withdraws or is discontinued from the study, the CRA will be informed immediately.

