10.1.7.2 Protocol Adherence and Deviations

The investigator and site personnel should conduct the study in compliance with the protocol and should use continuous vigilance to identify and report protocol deviations.

A protocol deviation is any change, divergence, or departure from the study design or procedures defined in the protocol that may be on the part of the investigator, site personnel, or the subject.

Important protocol deviations are a subset of protocol deviations that may significantly impact the completeness, accuracy, and/or reliability of the study data or that may significantly affect a subject's rights, safety, or well-being. For example, important protocol deviations may include

randomizing subjects in violation of key eligibility criteria designed to ensure a specific subject population or failing to collect data necessary to interpret primary endpoints, as this may compromise the scientific value of the study.

The investigator should not implement any deviation from the protocol without agreement from the sponsor and prior review and approval from the IRB/IEC of an amendment, except where necessary to eliminate an immediate hazard to a study subject. In the event of an important protocol deviation, the investigator will discuss the deviation with the sponsor's medical monitor and will come to an agreement as to whether the subject should be withdrawn from the study due to the important protocol deviation.

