Developing antibody incidence during the Post-randomization Period is defined as the number of subjects in the Safety Analysis Set (SAS) who have a positive result post randomization and have never tested positive (i.e., negative or no results) prior to the first dose of post-randomization IP divided by the number of subjects in the SAS who have at least a result post randomization.

End of Study (EOS) Date

The EOS date is the date recorded on the End of Study page of the CRF.

First Dose Date

It is defined as the date the subject received the first dose of IP.

First Post-randomization Dose Date

It is defined as the date the subject received the first post-randomization dose of IP.

Last Dose Date

It is defined as the date the subject received the last dose of IP.

Last Observation Carried Forward (LOCF)

Protocol Number: 20200497

Date: 10FEB2023 Page 14 of 36

A method of imputation where missing post-baseline data will be imputed by carrying forward the last non-missing post-baseline value for that endpoint. Baseline values will not be carried forward.

Neutralizing ADA Negative Subgroup

Defined as subjects in the subset of Safety Analysis Set (SAS) who have never tested positive (i.e. tested negative or no results) prior to the first dose of post-randomization IP, have at least one neutralizing ADA result post-randomization, and all available post-randomization neutralizing ADA results are negative.

Non Responder Imputation (NRI)

A method of imputation where a subject with missing post-baseline binary response data will be imputed as a non-responder, regardless of the reasons for missing data.

Study Analysis Visit

If more than one actual visit (including the unscheduled visits) falls within the same defined window, the visit closest to the target day with non-missing data will be considered for analysis. If two actual visit dates are at the same distance from the target day, the later visit with non-missing data will be considered for analysis.

For Efficacy, Vital, Safety Lab & PK

					Endpoint	
Study Analysis Visit	Target Day	Study Day	Interval (days)	Efficacy	Vital & Safety Labª	PK
Baseline ^b	1	≤1	NA	Х	Х	Х
Week 2	8	2-21	20		X	
Week 6	36	22-56	35	Χ	X	Χ
Week 12 ^b	78	57-91	35	Χ	X	Χ
Week 16	106	92-119	28	Χ	X	Χ
Week 20	134	120-161	42	Χ	X	Χ
Week 28	190	162-196	35		X	Χ
Week 30	14 days post week 28 dose	197-210	14	Х	Х	
Week 32	218	≥211	NA		Χ	

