6.5 Per-protocol Efficacy Analyses Set

The Per-protocol Efficacy Analysis Set consists of all subjects who are randomized and receive all assigned doses post-randomization and who have not experienced an important protocol deviation that may affect the evaluation of the efficacy endpoints. This analysis set will be used for primary analysis of the secondary efficacy endpoints and will be analyzed according to actual treatment received.

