9.3 Important Protocol Deviations and COVID-19 Related Protocol Deviations

Important Protocol Deviations (IPDs) data will be identified and recorded. The study team will conduct on-going reviews of the IPD data throughout the study and the resulting set of subjects to be included in the Per-protocol PK Parameter and Per-protocol Efficacy analysis sets. The Per-protocol analysis sets must be finalized prior to database lock of the final analysis.

For the Post-randomization Period, a summary of incidence of IPDs will be based on FAS and tabulated using number and percentage of subjects by deviation type (including COVID-19 related) and randomized treatment group. A listing of subjects with IPDs will be provided (with a flag indicating whether the deviation leads to exclusion from the Perprotocol PK Parameter or Efficacy analysis sets and a flag indicating whether an IPD is COVID-19 related) based on FAS.

For the Lead-in Period, a summary of incidence of IPDs will be based on LTS and tabulated using number and percentage of subjects by deviation type (including COVID-

Protocol Number: 20200497

Date: 10FEB2023 Page 27 of 36

19 related). A listing of subjects with IPDs (with a flag indicating whether an IPD is COVID-19 related) will be provided based on LTS.

All COVID-19 related Protocol Deviations (PDs) will be summarized by COVID-19 related deviation type for the FAS and LTS. A listing of subjects with COVID-19 related PDs will be provided for the FAS and LTS.

A listing of subjects affected by COVID-19 related study disruptions in the LTS for the Lead-in Period and in the FAS for the Post-randomization Period will also be provided, if applicable. The definition of "COVID-19 related study disruption" will be determined by the Amgen's study team.

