9.6.2.2 Secondary Analyses

These endpoints will also be summarized descriptively by actual treatment group based on Per-protocol Efficacy Analysis Set using observed data.

Sensitivity analyses will be conducted by repeating the models in section 9.6.2.1 using observed data in the FAS according to randomized treatment groups and in the Perprotocol Efficacy Analysis Set according to the actual treatment groups.

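### No planned week-30 efficacy analysis treats use of a prohibited psoriasis treatment as non-response by rule

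*Protocol*

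**What the plan says.** **Treatment rules.** Protocol 6.6.1 prohibits "Any other non study treatment for psoriasis, including UVA or UVB phototherapy and excimer laser (exclusion criterion 17) and topical therapies for psoriasis", apart from the topicals allowed under exclusion criterion 18, and also systemic and biologic psoriasis therapies. It attaches no analysis consequence. Protocol 7.2 lists "Requirement for alternative therapy per the investigator's determination" among the reasons for which a subject may be discontinued, at the investigator's discretion. Protocol 7.1 recommends that subjects who stop investigational product stay in the study where feasible, partly so that efficacy data can still be collected.

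**Main efficacy analysis.** SAP 9.6.2.1 uses the Per-protocol Efficacy Analysis Set. SAP 6.5 limits it to randomized subjects who "receive all assigned doses post-randomization and who have not experienced an important protocol deviation that may affect the evaluation of the efficacy endpoints". Protocol 10.1.7.2 defines the term only in general: "Important protocol deviations are a subset of protocol deviations that may significantly impact the completeness, accuracy, and/or reliability of the study data". A second limb of that definition concerns the protection of subjects. Its examples do not include prohibited medication. Classification is left to review: "The study team will conduct on-going reviews of the IPD data throughout the study" (SAP 9.3), with the per-protocol sets final before database lock.

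**Imputation.** Non-responder imputation (NRI) is defined in SAP 5.1 so that "a subject with missing post-baseline binary response data will be imputed as a non-responder, regardless of the reasons for missing data". SAP 9.6.2.1 applies NRI and last observation carried forward to missing week-30 values only. SAP 5.3 defines PASI response by percent improvement alone.

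**As-randomized analysis.** SAP 9.6.2.2 repeats the PASI models "using observed data in the FAS according to randomized treatment groups", and also on observed data in the per-protocol set. For sPGA and BSA, SAP 9.6.3 plans only the per-protocol set.

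**The concern.** A subject who loses response, takes another psoriasis treatment and still has a week-30 PASI presents an observed value that partly reflects that other treatment. NRI never reaches this subject, because nothing is missing. The per-protocol analysis may remove the subject, and the FAS models take the treated PASI at face value.

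The study is meant to show that switching does not reduce efficacy relative to continued use. Needing another psoriasis treatment is a direct sign of reduced efficacy. If it happened more often after switching, removing users and scoring them on a treated PASI would generally both pull the comparison toward no difference, which is the favourable direction here. The two planned analyses would then appear to corroborate each other while sharing the same blind spot.

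**Working it through.** **1. The plan's own figure.** The only sample-size statement is for PK: 342 randomized, at least 90% power, CV 53%, GMR 1, margin 0.8 to 1.25, 15% dropout (Protocol 9.3, SAP 3.2).

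- Evaluable: 342 × 0.85 = 290.7, about 145 per arm.
- Log-scale SD = √ln(1 + 0.53²) = 0.4976; SE = 0.4976 × √(2/145) = 0.0584.
- Power per endpoint = 2Φ(ln 1.25/SE − 1.645) − 1 = 97.0%; about 94.0% for both endpoints if independent.

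The figure is reproduced and this point does not touch it. No power or margin is stated for the week-30 efficacy endpoints.

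**2. Where a user of prohibited psoriasis treatment ends up.**

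| Situation | Per-protocol main analysis | FAS observed-data PASI models |
|---|---|---|
| Week-30 PASI present, a dose missed | Removed | Scored on treated PASI |
| Week-30 PASI present, all doses, use classed as an important deviation | Removed | Scored on treated PASI |
| Week-30 PASI present, all doses, not so classed | Scored on treated PASI | Scored on treated PASI |
| No week-30 PASI, all doses, not so classed | Non-responder by NRI | Not in model |
| No week-30 PASI, a dose missed | Removed | Not in model |

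The Schedule of Assessments has no PASI at the week 32/end-of-study visit, so that visit supplies no later value. In no row does the treatment itself make the subject a non-responder.

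**3. Illustrative size.** The documents give no response or use rates, so all inputs are assumed. Let p be the response rate in non-users (equal in both arms), r the response rate in users after the other treatment, and Δ the use rate in the switching group minus that in the continued-use group. The risk difference (switching minus continued use) is:

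- users counted as non-responders: −Δp
- per-protocol with users removed: 0
- observed scoring (FAS, or per-protocol with users kept): Δ(r − p)

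| p | Use, switching vs continued | Users as failures | Users removed | Observed scoring |
|---|---|---|---|---|
| 85% | 7% vs 2% | −4.25 | 0 | 0 (r = 85%) to −1.75 (r = 50%) |
| 80% | 5% vs 2% | −2.4 | 0 | −2.4, −0.9, 0, +0.6 (r = 0, 50, 80, 100%) |
| 80% | 10% vs 2% | −6.4 | 0 | −6.4, −2.4, 0, +1.6 (same r) |
| 80% | 2% vs 2% | 0 | 0 | 0 |

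First row: 0.93 × 0.85 − 0.98 × 0.85 = −4.25 points; 0.05 × (0.50 − 0.85) = −1.75 points.

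The amount hidden is therefore Δp when users are removed (0.02 × 0.75 = 1.5 to 0.05 × 0.92 = 4.6 points for p of 75% to 92% and Δ of 2 to 5 points) and Δr under observed scoring (nothing at r = 0; 8.0 points at Δ = 8 points and r = 100%).

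**4. Scale.** One subject in 171 is 0.58 points. The 90% CI half-width at p = 85% is 1.645 × √(2 × 0.85 × 0.15/171) = 6.35 points with 171 per arm, and 6.9 points with 145.

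**The case against.** **Efficacy does not carry the conclusion.** Protocol 2.1 describes efficacy as a descriptive, secondary assessment. The formal claim rests on the 90% CIs for AUCtau and Cmax (Protocol 9.2, SAP 2.2), and PASI has no hypothesis, margin or power. This stands and limits the point's weight.

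**The situation should be uncommon.** Other psoriasis treatment is prohibited, waivers are not allowed (Protocol 8), and Protocol 6.6.2 places alternative treatment for subjects who stop product after the end-of-study visit. A missing week-30 PASI is therefore the more expected route. This lowers the likely number of users but supplies no scoring rule for those who occur.

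**The events are partly visible.** SAP 9.3 tabulates important deviations by type and randomized group and flags exclusions; SAP 9.2 summarizes reasons for exclusion from each set; SAP 9.7.10 tabulates concomitant medication by actual group. This stands where use is classed as an important deviation. Users not so classed are not counted by randomized group.

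**Observed-data FAS plus per-protocol is a recognised pairing.** True, and there is no reason to drop either. The gap is that both can lean the same way.

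**A stronger reading is tempting**: that such a subject is always deleted or credited with benefit, so that no analysis ever counts a failure. The documents do not support it. A user still below the threshold at week 30 is an observed non-responder in the FAS models. Per-protocol removal needs a missed dose or a deviation decision. A user kept in that set with no week-30 PASI is a non-responder by NRI.

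**Conclusion.** The point holds in limited form. No planned week-30 efficacy analysis makes prohibited psoriasis treatment a non-response by rule, and the per-protocol handling of a fully dosed user rests on a deviation decision that the plan does not specify. If use were more frequent after switching, both the per-protocol and FAS analyses could move toward no difference. With equal use in both arms, little or nothing is hidden.

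In the unequal-use examples above, the hidden risk difference runs from 0 to 8.0 points. It depends entirely on assumed response and use rates and on equal response among non-users. The 1.5 to 4.6 points from removing users lie inside the 90% CI half-width of about 6.4 points.

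The reach is the secondary and other efficacy endpoints (PASI, sPGA, BSA). A reader might infer that the interchangeability conclusion is biased; it is not affected, because it depends on the PK intervals alone, and the sample size is unaffected too. This is a worthwhile clarification of supporting evidence, not a defect in the primary analysis.

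**What to change.** In SAP 9.6.2.2 and 9.6.3, keep the planned analyses and add one supplementary FAS analysis by randomized group. In it, a subject who received a Section 6.6.1 treatment for psoriasis after randomization and before the week-30 assessment is a non-responder for PASI 75/90/100 and sPGA 0/1. Use for another condition, such as a systemic corticosteroid given for a non-psoriasis reason, does not count. For sPGA this would be the first FAS analysis, since SAP 9.6.3 now uses only the per-protocol set.

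Also:

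- report the number of such subjects by randomized group, which also helps in reading PASI percent improvement and BSA change;
- decide and record before database lock whether such use is an important deviation for the Per-protocol Efficacy Analysis Set;
- confirm that phototherapy and laser dates are captured. Protocol 6.6.2 requires medications and vaccines to be recorded, but these are procedures and the CRF is not among the documents.

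The cost is SAP wording, one derived flag and slightly lower response rates in both groups in the supplementary analysis. No treatment rule changes.

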6.6.2 Prior and Concomitant Therapy

Prohibited treatments are described in Section 6.6.1.

Any other treatment (not explicitly excluded) which is considered necessary for the subject's welfare may be given at the discretion of the investigator. Allowed treatments include:

- Bland moisturizers/emollients (without urea or α- or β-hydroxy acids) are allowed, as needed, during the study.
- Upper mid-strength to least potent (class III to VII) topical steroids are permitted only on the palms, soles, face, and intertriginous areas.

 Otic, nasal, ophthalmic, or inhaled corticosteroids are not considered "systemic immunomodulating treatments" and are allowed during the study.

At screening, prior medication and COVID vaccination history will be documented.

Any vaccine or medication (including over-the-counter or prescription medicines, vitamins, and/or herbal supplements) that the subject is receiving at the time of enrollment or receives during the study must be recorded.

The medical monitor should be contacted if there are any questions regarding prior or concomitant therapy.

All subjects who discontinue investigational product should be offered alternative treatment, if applicable. Treatment should be given according to normal clinical practice after the EOS Visit.

6.7 Dose Modification

There are no dose modifications for investigational products (ABP 501 or adalimumab) in this study.

If the subject presents with a serious infection at the dosing visit(s), the administration of investigational product may be delayed (up to 5 days); and subjects with serious infections need to be monitored closely and investigational product should not be administered until the infection resolves.

In the case of delayed or missed dose for any reason, subsequent doses should be administered according to the original schedule (ie, at the planned time point relative to first dose) investigational product dose(s).

Any toxicities associated or possibly associated with investigational product treatment should be managed according to standard medical practice. A summary of expected adverse drug reactions is provided in the Investigator's Brochure. Adalimumab has a terminal -half-life of approximately 14 days, therefore discontinuation results in slow elimination over several months and will have no immediate effect.

If unmanageable toxicity due to investigational product occurs at any time during the study, treatment with the investigational product should be discontinued.

Clinical Study Protocol: 20200497

Final 1.0 Date: 03 Jun 2021 Page **39** of **87**

6.8 Intervention After the End of the Study

After completing dosing with investigational product at week 28 and the EOS Visit at week 32, subjects will have completed the study. ABP 501 or adalimumab will not be provided for post study use.

Final 1.0 Date: 03 Jun 2021 Page **40** of **87**

7 Discontinuation of Investigational Product and Subject Discontinuation

Subjects have the right to withdraw from treatment with investigational product, protocol procedures, or the study completely at any time and for any reason without prejudice to their future medical care by the physician or at the institution.

7.1 Discontinuation of Investigational Product

Subjects (or a legally acceptable representative) can decline to continue receiving investigational product or procedures at any time during the study but continue participation in the study. If this occurs, the investigator is to discuss with the subject the appropriate processes for discontinuation from investigational product and must discuss with the subject the possibilities for continuation of the Schedule of Assessments (Table 1-1) including different options of follow-up (eg, in person, by phone/mail, through family/friends, in correspondence/communication with other treating physicians, from the review of medical records) and collection of data, including adverse events, and must document this decision in the subject's medical records. Subjects who have discontinued investigational product and/or other protocol required therapies or procedures should not be automatically removed from the study. Whenever safe and feasible, it is recommended that these subjects remain in the study to ensure safety surveillance and/or collection of efficacy data, where possible. Reasons for early removal from -protocol-required investigational product(s) or procedural assessments may include:

- Decision by sponsor
- Lost to follow-up
- Death
- Adverse event
- Subject request
- Protocol deviation
- Noncompliance
- Pregnancy

Final 1.0 Date: 03 Jun 2021 Page **41** of **87**

7.2 Subject Discontinuation/Withdrawal from the Study

Participation in the study is strictly voluntary. Subjects have the right to withdraw from the study by his/her own request at any time and for any reason without any reprisal, and without prejudice to future medical care by the physician or institution.

Subjects unable to complete the week 12 visit will be discontinued from the study. However, subjects should return and complete EOS visit procedures. The lead-in period will occur from day 1 until randomization at week 12. All enrolled subjects not randomized at week 12 will be considered lead-in failures and the lead-in failure reason will be documented. Subjects terminating early from the study should complete all procedures scheduled for EOS Visit (ie, week 32) within 28 days after withdrawal/discontinuation if possible. Non-responders (defined as subjects achieving less than PASI 50 response at week 12 visit) will be discontinued from the study at week 12. These subjects will be asked to complete EOS Visit procedures.

Withdrawal of consent for a study means that the subject does not wish to receive further protocol required therapies or procedures, and the subject does not wish to or is unable to continue further study participation. Subject data up to withdrawal of consent will be included in the analysis of the study, and where permitted, publicly available data can be included after withdrawal of consent. The investigator is to discuss with the subject appropriate procedures for withdrawal from the study and must document the subject's decision to withdraw in the subject's medical records. If the subject withdraws consent for disclosure of future information, the sponsor may retain and continue to use any data collected before such a withdrawal of consent. If a subject withdraws from the study, he/she may request destruction of any samples taken and not tested, and the investigator must document this in the study center study records and notify the sponsor or designee. Although a subject is not obliged to give his/her reason(s) for withdrawing prematurely from a study, the investigator should make a reasonable effort to ascertain the reason(s), while fully respecting the subject's rights. Subjects who are withdrawn will not be replaced. Subjects who prematurely discontinue from the study cannot subsequently rejoin the study.

A subject may be discontinued from the study at any time at the discretion of the investigator for safety, behavioral, or administrative reasons, including, but not limited to:

Requirement for alternative therapy per the investigator's determination

Clinical Study Protocol: 20200497

Final 1.0 Date: 03 Jun 2021 Page **42** of **87**

 The subject develops a malignancy (exception: subjects may be allowed to continue if they develop no more than 2 non-melanoma skin cancers during the study)

- Adverse events or serious adverse events
- Any laboratory abnormalities that in the judgment of the investigator, taking into consideration the subject's overall status, prevents the subject from continuing participation in the study
- Any other reason relating to the subject's safety or integrity of the study data
- Noncompliance with study procedures
- Withdrawal of consent from the study
- Lost to follow-up
- Decision by sponsor/investigator
- Death

Refer to the Schedule of Assessments (Table 1-1) for data to be collected at the time of study discontinuation and evaluations that need to be completed.

If a subject withdraws or is discontinued from the study, the CRA will be informed immediately.

